- whether it constitutes a serious adverse event (SAE), if so report date should be provided
- action taken regarding study treatment
- whether other medication or therapies have been taken (concomitant medication/non-drug therapy)
- its outcome (not recovered/not resolved; recovered/resolved; recovering/resolving, recovered/resolved with sequelae; fatal; or unknown)

All adverse events should be treated appropriately by the PI or designee. Once an adverse event is detected, it should be followed until its resolution or until it is judged to be permanent, and assessment should be made at each visit (or more frequently, if necessary).

B. Serious Adverse Events:

An SAE is any adverse event which meets any one of the following criteria:

- is fatal or life-threatening
- results in persistent or significant disability/incapacity

- constitutes a congenital anomaly/birth defect
- leads to a hospitalization that is not related to a renal allograft biopsy, renal allograft rejection episode or infection

AEs and SAEs will be reported in accordance with the FDA Guidelines for Post-Marketing Reporting of Adverse Events 21 CRF 314.80 and 21 CRF 600.80

<http://www.fda.gov/medwatch/report/regs.htm>. Any serious adverse event or a non-serious adverse event that is related to the study and unexpected will be reported to the FDA, per reporting guidelines, as soon as possible, but no later than 15 working days. Any serious adverse event or a non-serious adverse event that is related to the study and unexpected will be reported to Novartis within 24 hours of occurrence. Further, all serious adverse events that are related to the study and are unexpected must be reported to The Medical University of South Carolina IRB within 10 days per The Medical University of South Carolina IRB Unanticipated Problems and Adverse Events Policy and Procedures reporting guidelines.

C. Pregnancy Reporting:

Any pregnancies occurring while the subject is on study treatment will be reported to Novartis within 24 hr of learning of its occurrence. The pregnancy should be followed up to determine outcome, including spontaneous or voluntary termination, details of the birth, and the presence or absence of any birth defects, congenital abnormalities, or maternal and/or newborn complications.

Statistical analysis:

Categorical data will be evaluated based on Fisher's Exact and Chi Square tests where appropriate; descriptive statistics will be used for continuous variables to describe the two patient populations and primary outcomes in each group (% change in interstitial fibrosis and eGFR from month 3 to month 12). Student's T-test or comparable non-parametric tests (such as the Wilcoxon Rank Sum test) will be used to compare the groups for these continuous variables. Patients will be analyzed based on an intent-to-treat basis, except when prohibited by lack of follow-up 12 month biopsies. Kaplan-Meier curves with the log rank test will be used to compare patient and graft survival, acute rejection free survival, and *de novo* donor specific antibody free survival. A p-value of <0.05 will be considered statistically significant. Slope change of eGFR from 3 months to 12 months post-transplant will be calculated and compared as well.

For the genomic comparisons, patients will be grouped based on the presence or absence of known single nucleotide polymorphisms and compared for primary outcomes. If significant baseline differences are noted between groups, multivariate analysis will be conducted to control for these differences. Similar analyses will be conducted for change in mRNA expression and change in urinary proteomic excretion between month 3 and month 12.

This will be an intent-to-treat analysis with all patients undergoing randomization included in the final data analysis, even if removed from study or control medication. Patients screened and consented, but not randomized will be tracked for reasons of non-randomization, but will not be followed for clinical outcomes or included in the final analysis. These patients will be

replaced to insure a total of 60 patients (30 in each group) are randomized and followed to meet study power and sample-size.

Sample size and power: A total of 60 patients, 30 *randomized* in each arm, will provide 89% power (alpha=0.05, two-sided) to detect a significant difference in the percent change in the quantity of interstitial fibrosis between groups when comparing the three month and 12-month protocol biopsies. These calculations used the following assumptions: 10% drop out rate for each group (27 patients in each group will have baseline and follow-up biopsies), with a $64\pm41\%$ change in degree of fibrosis in the control arm and a $13\pm71\%$ change in fibrosis in the investigational arm.

Evaluation schedule:

Assessments		Pre-Txp	Day Post-transplant							Week Post-Txp		Month Post-transplant			
Time Frame			1	2	3	4	5	6	7	2	4	3	4	6	12
RANDOMIZATION												X (10-16 week window)			
History and Physical ²		X								X	X	X	X	X	X
Vital Signs		X	X	X	X	X	X	X	X	X	X	X	X	X	X
Protocol Kidney Biopsy												X			X
Donor Specific Antibody Analysis												X			X
Pregnancy testing ⁷		X	X (anytime between day 1-7)											X	X
Serologies ¹		X													
Laboratory Assessment	CBC and Chem-7 ⁴	X	X	X	X	X	X	X	X	X	X	X	X	X	X
	Total cholesterol, HDL, LDL, triglycerides ³	X										X	X		X
	Spot Urine Protein/Creatinine Ratio											X	X		X
	Tacrolimus levels ⁵			X	X	X	X	X	X	X	X	X	X	X	X
	Everolimus levels											X	X	X	X
Clinical assessment ⁶		X	X	X	X					X	X	X	X	x	X
EKG		X													
Estimated GFR		X	X	X	X	X	X	X	X	X	X	X		x	X
Genomic, RNA and proteomic analysis ⁴												X			X
Applanation tonometry using pulse wave velocity and augmentation index		One Baseline Measurement										X			X

Foot notes:

- Includes testing for CMV, Epstein-Barr, hepatitis B & C and HIV for donor and recipients (from evaluation or within one year pre-transplant if the results were negative at pre-transplant evaluation)
- Within 48 hours prior to transplant
- Fasting for at least 8 hours
- Includes genetic SNP analysis, mRNA expression, and urinary proteomic analysis
- Tacrolimus concentrations will be measured daily during the first week post-transplant once tacrolimus is initiated
- Includes assessments of blood pressure, weight changes, arterial stiffness measurement, adverse events, study drug doses, allograft rejection, infection, need for dialysis, hospitalization, re-transplant status, and other immunosuppressant medications
- Includes pregnancy test for females of child-bearing potential

Key references:

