1. Measure and compare the change in interstitial fibrosis (morphometric analysis of trichrome stained slides) at one-year post-transplant in patients converted to everolimus, low intensity tacrolimus and prednisone versus the standard of care tacrolimus, mycophenolate and prednisone regimen.

Secondary objectives:

1. Measure and compare the estimated GFR (using the 4-variable modified MDRD equation) in patients converted to everolimus, low intensity tacrolimus and prednisone versus the standard of care tacrolimus, mycophenolate and prednisone regimen, both at one year and two years post-transplant.
2. Compare the patient and graft survival rates at one-year post-transplant in each group.
3. Measure and compare the rates of immunosuppressant discontinuation and modification for each group.
4. Measure and compare the incidence of significant immunosuppressant-related adverse drug reactions for each group.
5. Compare the rates of post-transplant infections, including CMV, BK, and admissions to the hospital for infectious causes in each group.

Endpoints 6 through 10 are exploratory:

6. Measure and compare the rates and quantity of *de novo* donor specific antibody formation at one-year post-transplant in each group; this will address the important clinical question of the risk of humorally mediated alloimmune events with CNI minimization.
7. Determine the impact of gene variants for donor APOL1, donor ABCB1, recipient cytochrome P450 3A5, and donor and recipient angiotensin receptor and angiotensin converting enzyme on the primary objectives. This endpoint addresses pathways that could potentially impact outcome but are not measured by traditional risk factors and explanatory variables such as rejection and immunosuppressant concentrations.
8. Examine changes in gene expression and urinary proteomics using high throughput methods on peripheral blood, renal biopsy tissue and urine. The rationale underlying this endpoint is that these markers could yield potential biomarkers that may be used as a companion diagnostic aid in selecting patients at particularly high risk for renal progression or CNI nephrotoxicity.

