of induction will be based on the patient's immunologic risk (PRA) or risk of developing DGF. Tacrolimus doses will be adjusted to obtain target blood concentrations 5-12 ng/mL (using LCMS) for the first 3 months post-transplant. In the investigational arm, tacrolimus will be adjusted to obtain target trough concentrations of 2-5 ng/ml after 3 months post-transplant, once the patient is transitioned from mycophenolate to everolimus. The goal everolimus trough concentrations in this group will be 3-8 ng/mL (using LCMS). In the standard arm, tacrolimus doses will be adjusted to maintain a trough concentration of 5-12 ng/mL throughout the study period. Dose adjustments for immunosuppression will be allowed based on side effects or toxicities, at the clinical judgment of the primary investigator. Trough monitoring of mycophenolic acid will not be performed unless clinically warranted and dosage adjustments from such levels will be made only with consent of the study primary investigator. In the investigational arm, everolimus will be initiated at month 3 post-transplant at a dose of 1.25 mg twice daily in African-Americans and 1 mg twice daily in non-African-Americans. Doses will be adjusted to maintain trough concentrations of 3-8 ng/ml. Corticosteroids will be based on institutional protocol and will be continued in all patients at a minimum dose of 5 mg daily of prednisone or equal potent exposure if a different corticosteroid is utilized. Antimicrobial and anti-fungal prophylaxis will be administered based on institutional protocol.

Whole blood trough level monitoring of tacrolimus will be performed as follows, at a minimum of: post-operative day 3, 5, and 7, weeks 2, 3, 4, and months 2, 3, 6, 9 and 12. Everolimus whole blood trough level monitoring will be performed as follows, at a minimum of: post everolimus conversion day 4, weeks 1, 2, 3, 4 and months 3, 6, and 9. Tacrolimus and everolimus dosing may be adjusted as medically required for toxicity or rejection.

Study duration: 42 months total, with 6 months for start-up and initiation, 18 months for patient recruitment and randomization, 12 months of patient follow-up, and 6 months for data analysis and final report/manuscript preparation.

Study design: Prospective, randomized, comparative efficacy, open label study.

Study Procedures and Definitions:

A. Supplementary medications:

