Patients will receive anti-infectives as per post-transplant protocol regimens as per usual care. Anti-infective prophylaxis: prophylactic antifungal therapy will consist of Nystatin 5 mL swish and swallow by mouth four times daily for 30 days post-transplant. Alternative therapies may be utilized based upon patient tolerability. Patients will receive PJP prophylaxis with sulfamethoxazole/trimethoprim single-strength tablet once daily for 6 months post-transplant. Sulfa allergic patients may receive either inhaled Pentamidine or oral daily Dapsone therapy depending on patient and physician preference. All patients at moderate (R+) or high-risk (D+/R-) for CMV infection will receive oral valganciclovir therapy for 3 to 6 months post-transplant.

B. Clinical and Laboratory Assessments:

Laboratory assessments: Laboratory evaluations will be performed at certified laboratories according to the study schedule. Required tests are specified in the study flow chart (see Appendix I).

Clinical assessments: All patients will undergo clinical evaluation by the investigator or the investigator's designee at the times specified in the study flow chart (see Appendix I). Clinical evaluations will include assessments of sitting blood pressure, patient weight changes, GI symptoms assessment, serious adverse events, study drug doses and concentrations, allograft rejection, infection, need for dialysis, hospitalizations; re-transplant status, and other immunosuppressant medications.

Graft function assessment: To monitor graft function, serum creatinine will be assessed immediately post-operatively to establish initial renal function. Creatinine clearance will be assessed at 1 week, 3 months, 6 months and 12 months using the abbreviated MDRD equation.

Acute renal dysfunction: renal dysfunction will be monitored by serial measurements of serum creatinine. All episodes of renal dysfunction defined as an incremental increase in serum creatinine concentration 20% above baseline or ≥ 0.4 mg/dL will be evaluated for rejection by renal biopsy and ultrasound, after the exclusion of other causes renal graft dysfunction (such as infection, dehydration and CNI toxicity).

C. Definition and diagnosis of rejection episodes:

Acute Rejection is defined as: elevation of serum creatinine of at least 20% above baseline or an absolute increase of greater than 0.4 mg/dl with renal allograft biopsy showing grade $\geq 1A$ rejection by Banff criteria.

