Applanation tonometry will be performed by placing a micromanometer-tipped probe against the skin surface over the artery of interest and obtaining pressure waveforms transmitted through the skin surface. Pressure waveforms will be recorded during an 8-second period using a high-fidelity SPC-301 micromanometer (Millar Instrument, Inc., Houston, TX, USA) interfaced with a computer employing SphygmoCor, version 9.0 software (AtCor Medical Pty. Ltd., West Ryde, New South Wales, Australia). To determine aortic BP, the pulse wave obtained from radial tonometer recordings will be calibrated by manual measurement (auscultation) of brachial BP taken immediately before the recordings. The radial pressure waveform will be converted into a central (aortic) waveform using a validated generalized transfer function (GTF) incorporated in SphygmoCor software. Central aortic systolic and diastolic BP will be derived from the aortic waveform and PPc will be calculated from the difference.

Safety Assessment Definitions:

A. Renal Function:

Renal function will be calculated by the eGFR using the 4-variable MDRD formula. Time points for calculations are delineated in the Study Evaluation Schedule located in the Appendix at the end of this protocol. The primary renal function assessments utilized for safety and efficacy analyses will be the eGFR at baseline (randomization) and at 12 months post-transplant.

B. Physical Examination:

A thorough physical assessment will be performed at screening/randomization and at months 3, 4, 6 and 12 post-transplant. Significant findings that are present prior to the start of the study will be included in the Relevant Medical History/Current Medical Conditions on the CRF. Significant findings made after the start of study medication which meet the definition of an AE will be recorded in the AE CRF.

C. Vital Signs:

Vital signs (radial pulse rate and blood pressure) will be recorded as indicated in the Study Evaluation Schedule located in the Appendix at the end of this protocol. Blood pressure and pulse rate will be assessed at the same arm each time of determination and after the subject has rested in the sitting position (may be supine if during hospitalization) for at least five minutes. Measurements will be recorded on the CRF.

D. Height and Weight:

Height and weight will be measured and recorded at screening and during follow-up visits when physical exams are performed. Results will be recorded on the CRF.

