E. Laboratory Evaluations:

All laboratory measurements will be performed at MUSC or referral centers that are routinely used as part of usual follow-up care. Specific information regarding the types and schedule of laboratory assessments can be found in the Study Evaluation Schedule located in the Appendix at the end of this protocol. Laboratory measurement results and date of collection will be recorded for the baseline and follow-up time points within the CRFs. Sample collection and analysis for the proteomics, genomics and gene expression analyses will be conducted as described in the above sections.

F. Pregnancy, contraception and assessment of fertility:

Pregnancy testing (serum) will be carried out for all females of child-bearing potential as described in the Appendix at the end of this protocol. Testing will be part of routine follow-up care and will be conducted pre-transplant, within 7 days of transplant and at months 6 and 12 post-transplant.

Females of reproductive potential taking mycophenolate must receive contraceptive counseling and use acceptable contraception as delineated below for the entire time while on mycophenolate and for 6 weeks after stopping mycophenolate, unless the patient chooses abstinence (she chooses to avoid heterosexual intercourse completely). Females of reproductive potential taking everolimus must receive contraceptive counseling and use acceptable contraception as delineated below for the entire time while on everolimus and for 8 weeks after stopping everolimus, unless the patient chooses abstinence (she chooses to avoid heterosexual intercourse completely).

Acceptable contraception methods for females of reproductive potential

Option 1 (monotherapy methods):

1. Intrauterine devices (IUDs)
2. Tubal sterilization
3. Patient's partner had a vasectomy

Option 2 (Choice one from category A AND one from category B):

1. Category A:
 - a. Estrogen and progesterone
 - i. Oral contraceptive pill
 - ii. Transdermal patch
 - iii. Vaginal ring
 - b. Progesterone only
 - i. Injection
 - ii. Implant
 - c. Barrier method
 - i. Diaphragm with spermicide
 - ii. Cervical cap with spermicide
 - iii. Contraceptive sponge
2. Category B:
 - a. Male condom
 - b. Female condom
 - c. Diaphragm with spermicide (for use with hormone therapy)
 - d. Cervical cap with spermicide (for use with hormone therapy)
 - e. Contraceptive sponge (for use with hormone therapy)

G. Choice of Safety measurements:

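### Secondary objective 1 promises a two-year eGFR comparison, but the plan's visits, follow-up period and analyses stop short of two years

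*Combined protocol and SAP*

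**What the plan says.** Secondary objective 1 compares eGFR, by the four-variable MDRD equation, "both at one year and two years post-transplant". The operative sections read differently:

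- **Study duration:** after 6 months of start-up, "18 months for patient recruitment and randomization, 12 months of patient follow-up, and 6 months for data analysis", for a stated total of 42 months.
- **Clinical and Laboratory Assessments, graft function:** "Creatinine clearance will be assessed at 1 week, 3 months, 6 months and 12 months using the abbreviated MDRD equation".
- **Safety Assessment Definitions, A. Renal Function:** "Time points for calculations are delineated in the Study Evaluation Schedule located in the Appendix at the end of this protocol". The same paragraph names baseline (randomisation) and month 12 as the main renal function assessments.
- **Evaluation schedule:** the "Estimated GFR" row is marked pre-transplant, on days 1 to 7, at weeks 2 and 4, and at months 3, 6 and 12. Month 12 is the last column of the table.
- **Statistical analysis:** eGFR change is taken from month 3 to month 12, and "Slope change of eGFR from 3 months to 12 months post-transplant will be calculated and compared as well".

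Other text also stops at one year: patient and graft survival are compared then, malignancies are recorded up to then, and the minimum tacrolimus trough schedule ends at month 12.

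**The concern.** A stated secondary comparison has no assessment, no follow-up period and no analysis behind it. Staff who follow the plan exactly would collect no data for it.

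Improvement in GFR is part of the trial's stated hypothesis, so this is not a peripheral outcome. Without a decision in advance, the trial ends in one of two ways. The objective may go unreported without explanation. Or two-year values may be gathered afterwards with no set window, closing date or rule for who counts, and the number of patients would then depend on how recruitment happened to run.

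Closing by calendar date would affect both arms alike, so on that score the loss is mainly precision. Uneven availability of routine values in an open-label trial is a separate risk, which the plan does not address.

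**Working it through.** **The plan's own figures.** The stated duration adds up: 6 + 18 + 12 + 6 = 42 months. The stated 89% power is for the fibrosis endpoint only. With 27 evaluable patients per arm, the difference is 64 − 13 = 51 points and the SD is √((41² + 71²)/2) = 57.97. The normal approximation gives 89.8% and the noncentral t gives 88.7%, so the figure reproduces. No power is stated for eGFR at either time point.

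**Scheduled values.** The eGFR row has 13 marks, none at or after month 24. Scheduled two-year values: 0 of 60.

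**Follow-up counted from randomisation.** Randomisation is at about 12 weeks, within a 10 to 16 week window (2.3 to 3.7 months). Twelve months later is month 12 + 2.3 = 14.3 to 12 + 3.7 = 15.7 post-transplant. That is 8.3 to 9.7 months short of two years.

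**Follow-up counted on the project calendar.** Recruitment occupies project months 6 to 24. Taking randomisation at 3 months post-transplant, two years needs 24 − 3 = 21 further months (20.3 to 21.7 across the window). A patient randomised at the end of recruitment reaches two years at 24 + 21 = project month 45, which is 3 months after the study ends.

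Suppose data collection for everyone ran to one closing month C. The plan does not say this; it is an assumption. The fraction of the recruitment period early enough to reach two years is x = (C − 21 − 6)/18. The share of patients is then x under uniform accrual, x² if accrual rises linearly from zero, and 1 − (1 − x)² if it falls linearly to zero.

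| Closing month C | x | Uniform, of 60 | After 10% loss | Rising | Falling |
|---|---|---|---|---|---|
| 33 (last month-12 visit, 24 + 9) | 0.333 | 20 | 18 | 11% | 56% |
| 36 (end of follow-up block) | 0.500 | 30 | 27 | 25% | 75% |
| 42 (end of study) | 0.833 | 50 | 45 | 69% | 97% |

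The 10% loss is the plan's dropout figure for paired biopsies, borrowed here as an assumption.

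**Duration needed for all patients.** With the other blocks unchanged: 6 + 18 + 21 + 6 = 51 months, 9 more than stated.

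**The case against.** Four points can be made for the plan.

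- **Two-year values may exist anyway.** Laboratory Evaluations says testing is done at the trial centre or at referral centres "routinely used as part of usual follow-up care", and transplant recipients may well have creatinine measured after month 12. But those words describe which laboratories are used. That later values exist is an inference, and the plan does not say they will be collected or analysed. The count of 0 of 60 therefore means no scheduled value, not that no patient could reach two years.
- **The 12 months of follow-up can be read as a project block** ending at month 36. On that reading about 30 of 60 patients would have passed two years under uniform accrual. That is still only half, with no eGFR scheduled for them at that point.
- **The lists are not exhaustive.** The graft function paragraph omits early eGFR marks that the schedule contains, and the study duration, follow-up and tacrolimus text do not map perfectly onto the schedule: month-9 tacrolimus levels are required, yet there is no month-9 column. Absence from one list is weak evidence. Here, though, the schedule, the renal function section, the follow-up period and the statistical section all stop short of month 24.
- **The accrual range of 11% to 97% rests on assumptions.** That is fair. It shows only that the two-year sample would be unpredictable without a rule. The main finding does not depend on it.

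It is also true that the matter is confined to one secondary time point and that one-year eGFR is properly scheduled and analysed.

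**Conclusion.** The concern holds. The two-year part of secondary objective 1 contradicts the rest of the plan and cannot be delivered by following it: 0 of 60 patients have a scheduled two-year eGFR. On neither reading of the follow-up period do all patients reach two years. That conclusion assumes recruitment uses its full 18 months and randomisation falls at about 3 months post-transplant; the count of scheduled values needs neither assumption.

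The documents do not show whether the objective or the timeline is the error. The point should be corrected, but its reach is limited: the primary endpoint, its sample size and the one-year eGFR comparison stand.

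**What to change.** Reconcile the passages in one of two ways.

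**(a) Remove the two-year comparison** from secondary objective 1, and record the change and its reason in an amendment. The cost is one stated secondary time point and the amendment. The present 42 months then suffice.

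**(b) Keep it and make it deliverable.** Add a month-24 eGFR, from routine-care creatinine, to the evaluation schedule with a stated time window. Add the between-arm comparison to the statistical section, and say how death or graft loss before month 24 and missing routine values are handled. Extend follow-up to about 21 months after the last randomisation. The cost is an amendment, chart abstraction and about 9 more calendar months, for 51 in total. Alternatively, report one-year results on the present timeline and two-year eGFR in a supplement after about project month 45.

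Neither option changes the primary endpoint or its sample size.
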